10.0 Study Design / Methods

- Potential subjects will be approached for informed consent as directed in sections 8.0 and 9.0. Pertinent project information, risks, and time commitment will be relayed to subjects. If subjects show interest in participating, they will be given consent forms to either sign or bring home for consideration. A urine pregnancy test will be administered to these patients to confirm that they can be included in the study.
- If the patient is eligible for the study, he or she will be randomly assigned to one of two groups. They will have a 50/50 chance of being in either group. Neither the researchers nor you will make the choice to which group you are assigned. The two groups are Group A (cholesterol/lovastatin) and Group B (lovastatin only). The patient will not be informed of which group they are in and will not be informed of what their study medication is, allowing single-blinding. Researchers will not be masked.
- Enrolled subjects will be followed up at monthly intervals for three months via virtual check-in using an MUSC approved HIPAA compliant technology. At each visit, participants will undergo brief, limited physical examination (in order to determine disease severity and affected body surface area); additionally, clinical photographs of the lesion will be obtained in clinic or shared virtually with the investigators via secure email (sent to MUSC Outlook email). The physical exam will occur in-person or by using the virtual visit technology, which allows us to see the patient and visualize their skin findings.. Photographs will be stored in the coded study-specific medical record for further analysis of lesion features.
- At each visit a Patient Quality of Life, Physician Global Assessment Scale, and Actinic keratosis Field Assessment Scale will be administered.
- Patients will be contacted via virtual check-in visits at weeks 4, 8, and 12. Patients will be asked about compliance and any adverse effects experienced. Patients are also encouraged to contact [name] at any given point during the study if they think they are experiencing study-related side effects. Immediate consultation will follow to determine the severity of such event and necessary impacts on patient health and participation. Participants will also be contacted by phone by study team member to assess for any adverse effects at weeks 2 and 6 of treatment.

- Compounded topical medication prescribed to subjects will be self-applied twice daily. These medications will be prepared by Tidewater Pharmacy in Mount Pleasant, SC or Chemistry Rx in Philadelphia, PA. They will be prepared so the study will remain single-blinded (only investigators know which study drug they are receiving) and associated costs will not be covered by the research budget. The cost of the medication will be approximately \$85 when dispensed by Tidewater Pharmacy, or \$110 when dispensed by Chemistry Rx. The differences in costs are attributed to shipping and pharmacy fees.
- Both pharmacies will be compounding the drugs to be used in this study, and the compounding formula (recipe) will be identical between these two compounding pharmacies.
- Enrollment and prescription drug delivery to other states will not be performed until the respective state pharmacy boards confirm the legality of clinical telehealth interventions and out-of-state pharmacy prescriptions. All state and federal guidelines will be followed according to their regulations and recommendations.
- Patient prescriptions will be called in to their respective pharmacies by credentialed study team members after enrollment is completed. Individual prescriptions will be called in to the aforementioned pharmacies so that the pharmacies can individually ship the medication to the respective participant. Both pharmacies are well aware of the study protocol and procedures for sending the prescription. This will occur by standard procedure of calling medications for patients:
 - 1. The study team member will call the pharmacist to inform them that a participant has been enrolled and ready to receive one of the two single-blinded drugs. The lovastatin/cholesterol combination has been assigned the arbitrary codename “RDC100”, and the lovastatin alone medication has been assigned the arbitrary codename “RDC15”. On the prescription label there will be the codename, application instructions, and storage instructions.
 - 2. Per standard procedure of calling in a prescription, the study team member will verbally inform the Tidewater/Chemistry Rx pharmacist of the patient name, birthday, and phone number so that the medication can be prescribed and so that the patient can be contacted by the pharmacist for shipping and payment purposes.
 - 3. The pharmacist will contact the patient over the phone in order to complete the medication payment over the phone and to identify the address to which the medication will be sent to.
 - 4. The subject will inform the study team member upon receipt of the medication, confirm that they received the correct, randomized medication.
 - 5. All of the information related to drug disposal and reception will be recorded on the coded Drug Accountability Sheet, which is located separately in the secure box drive.

- Medications will be able to be shipped to all continental US states by Chemistry Rx, except Alabama. This is because Chemistry Rx does not have the license to dispense to Alabama. Therefore, any participant reliant upon an Alabama address to receive their medication will not be allowed to participate in this study.
- Dermoscopic and clinical photographs will be subsequently analyzed for the presence of cornoid lamella. The team will record any additional dermoscopic or clinical feature that may arise during the analyses.
- Frequency of dermoscopic and clinical features will be analyzed against clinical involution to find possible predictors.
- Procedures during the day of imaging:

The doctor will identify the lesion(s) that will be analyzed.

The lesion(s) will be measured and clinical and dermoscopy photographs will be taken. Facial images might be taken to assess lesions on the head area.

Schedule of events:

Event	Screening Baseline Visit 1	Week 4 (virtual)	Week 8 (virtual)	Week 12 (virtual)
Informed consent	X			
Eligibility Assessment	X			
Demographics	X			
Physical Examination	X			
Clinical photograph & Scale (3x) administration	X	X	X	X
Dermoscopic photograph	X			
Adverse events monitoring	X	X	X	X

11.0 Data Management

- Continuous data will be summarized using descriptive statistics (number of values, means, standard deviation, median, minimum and maximum). Categorical data will be summarized using frequency tables (frequencies and percent).

- We are comparing before and after photographs from the same patient, hence we employ analysis by paired t-test to compare baseline data with data after treatment.
- Coded dermoscopic and clinical photographs may be obtained for further analyses. Files with patient images will be stored in a secure departmental drive that will only be accessible to study team members by their unique MUSC ID and password.
 - Photos shared directly via email to study team members will be also be uploaded to the participants respective coded folder on the Box drive.
 - These emailed photos (sent by the participant personal email) must be de-identified close up photos of the participants legs or arms, and sent only to study team members secure MUSC-assigned Outlook email addresses. Photos that do not fit this criteria will be deleted upon receipt and not used in the study.
- All subject medical record information and data collection will be coded and stored on an MUSC Box drive only accessible to study team members, and will be protected by two-factor authentication.

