2.0 Background

Porokeratosis is a premalignant condition with a malignant transformation rate of 7.5%¹. Variants include disseminated superficial actinic porokeratosis (DSAP), disseminated superficial porokeratosis, porokeratosis of Mibelli, porokeratosis palmaris et plantaris disseminate, porokeratosis ptychotropa, and linear porokeratosis.

Porokeratosis is a rare condition involving clonal proliferation of abnormal keratinocytes that can be inherited or acquired. DSAP is the most common type of porokeratosis. It is described as a well circumscribed, erythematous macule with a peripheral rim of hyperkeratosis, also referred to as the coronoid lamella. While typically benign, lesions may develop into squamous cell carcinoma or Bowen's disease¹. The lesions typically spare the palms and soles and are most prevalent on the extensor surfaces and back. DSAP typically presents in patients in their 30s and 40s who have a history of extensive ultraviolet radiation exposure. It is estimated to occur in a female to male ratio of 1.8:1².

The exact pathogenesis for DSAP is currently unknown, however, the mevalonate genetic pathways are suspected to play a role in development. In one study, at least one mutation in the mevalonate pathway was found in 98% of familial cases and 70% of sporadic cases³. Treatment usually consists of destruction of the lesion utilizing cryotherapy, photodynamic therapy, carbon dioxide lasers, 5-fluorouracil. However, recent observations have suggested that various porokeratosis variants arise in areas affected by second-hit mutations in genes encoding components of the mevalonate pathway. Consequently, investigators from Yale University successfully treated a series of patients with topical cholesterol/lovastatin which resulted in complete clearance of DSAP lesions after 4 weeks of treatment⁴.

It is hypothesized that statins will block the accumulation of toxic metabolites in the mevalonate pathway, while topical cholesterol will provide the essential nourishment to the cells⁴. This study will provide a larger sample size and allow us to observe more definitive outcomes of the stain/cholesterol therapy.

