4.0 Study Endpoints

- Percentage of clearance of disseminated superficial actinic porokeratosis lesions after 12 weeks of therapy
- Validated scale changes: Patient Quality of Life (RAND36, DLQI), Physician Global Assessment Scale (DSAP-PGA), Actinic Keratosis Field Assessment Scale
- Clearance of coronoid lamella on dermoscopy (or photograph) after 12 weeks of therapy.

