6.0 Number of Subjects

Approximately 50 subjects will be recruited.

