2.1 Sample Size Calculation

DSAP is a rare disease that effects people from a wide geographical region. The goal sample size for the study was to recruit 50 subjects, however, due to recruiting limitations and state regulations, we were only able to enroll 31 patients. No formal sample size calculation was necessary as this study is first of its kind.

3. Aims and Objectives

• The purpose of this study is to evaluate the effectiveness of cholesterol/lovastatin versus lovastatin alone to treat porokeratosis. Our working hypothesis is that both topical cholesterol/lovastatin and lovastatin alone are helpful in treating patients with disseminated superficial actinic porokeratosis (DSAP).

DSAP: Single-Blinded randomized trial

Aims:

- 1. To evaluate the response (lesion size, color, patient quality of life) to treatment with topical cholesterol/lovastatin and lovastatin alone in a series of patients with the diagnosis of DSAP.
- 2. To characterize lesion patterns following topical treatment and patterns of lesion regression.
- 3. Access quality of life outcomes through RAND36 and DLQI surveys.

4. Outcomes

This section will present the outcomes investigated to answer the study aims and objectives. The analyses are described in section 6 Analyses.

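### Cornoid-lamella clearance is a protocol endpoint with no between-arm analysis; the only test that could reach it is a before-after paired t-test, which can mislead if readings miss the lamella more often at week 12 than at baseline

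*Protocol*

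**What the plan says.** Protocol section 4.0 lists as an endpoint "Clearance of coronoid lamella on dermoscopy (or photograph) after 12 weeks of therapy". Section 10.0 says how it is read: "Dermoscopic and clinical photographs will be subsequently analyzed for the presence of cornoid lamella". That is a present/absent reading.

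Protocol section 11.0 holds the protocol's whole statistical plan. It names one test, which sets baseline against post-treatment values: "We are comparing before and after photographs from the same patient, hence we employ analysis by paired t-test to compare baseline data with data after". The bullet before it says: "Categorical data will be summarized using frequency tables (frequencies and percent").

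The SAP repeats the photograph reading in section 2 but does not list lamella clearance among the outcomes in 4.1 or 4.2, and section 6 gives no analysis of it. Its comparisons across drug are a Drug by Time repeated-measures ANOVA on DSAP-GASI (6.1) and a chi-square on patient self-report (6.2). Section 6.2 also names a repeated-measures ANOVA for the quality-of-life scales. Rim elevation is one graded component of DSAP-GASI (4.1), and that score is read by two blinded physicians (6.1).

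Both documents give the purpose as evaluating the combination against lovastatin alone. In both schedules of events, dermoscopic photographs appear at baseline only and clinical photographs at every visit. Week 12 is virtual.

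**The concern.** Randomisation lets this trial ask whether adding cholesterol clears more lamellae than lovastatin alone. On this endpoint nothing in either document asks it. The one test that could be applied compares each patient with his or her own baseline, with no untreated group to show what reading error or natural change would produce.

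A present/absent reading makes this worse. The protocol's Background describes the lesion by its "peripheral rim of hyperkeratosis, also referred to as the coronoid lamella", and clearance can be scored only where the lamella was there to begin with. If every scored lesion starts as present, no paired difference can go the other way. Every lamella missed at week 12 then counts as benefit, and no opposite error offsets it. The risk is a reported significant clearance that partly reflects image quality and says nothing about which treatment is better.

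**Working it through.** Neither document states a sample size calculation, a clearance rate or a p-value for this endpoint, so there is no plan figure to reproduce.

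**Inputs**
- n = 31, from SAP 2.1 ("we were only able to enroll 31 patients"); the protocol planned more ("Approximately 50 subjects will be recruited").
- Assumed: one present/absent reading per patient, all 31 evaluable, two-sided alpha 0.05, arms of 16 and 15.
- Miss rates (a lamella that is there but read as absent) are assumptions, shown over a range.

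**1. Threshold when baseline is all present.** With k patients changing to absent and n − k unchanged, the mean change is k/n and

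t = sqrt(k(n − 1)/(n − k)), with n − 1 degrees of freedom.

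- k = 3: sqrt(3 × 30/28) = 1.793, p = 0.083
- k = 4: sqrt(4 × 30/27) = 2.108, p = 0.043

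Four absent readings suffice. The threshold is also 4 at the other sizes checked, from n = 15 (p = 0.041) to n = 50 (p = 0.044), so losing patients without photographs does not move it. It does depend on using a t-test for 0/1 data: exact McNemar gives 2 × 0.5^4 = 0.125 at 4 and needs 6 (2 × 0.5^6 = 0.031).

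**2. False rejection with no true clearance and no misses at baseline.** The number read as absent is Binomial(31, q), where q is the week-12 miss rate. The test rejects when at least 4 are absent.

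| q | P(at least 4 of 31) |
|---|---|
| 5% | 7% |
| 10% | 38% |
| 15% | 70% |
| 20% | 89% |

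**3. False rejection when lamellae can also be missed at baseline.** With independent miss rates q0 at baseline and q1 at week 12, a patient goes from present to absent with probability (1 − q0)q1 and from absent to present with probability q0(1 − q1). With b and c such patients,

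t = (b − c)/sqrt(n s²), where s² = [(b + c) − (b − c)²/n]/(n − 1).

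The multinomial probabilities are summed over all (b, c) with |t| > 2.042.

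- q0 = 5%, q1 = 15%: transition probabilities 0.95 × 0.15 = 0.1425 and 0.05 × 0.85 = 0.0425; rejection about 24%.
- q0 = q1, from 5% to 20%: rejection about 3% to 5%, so no inflation.

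The inflation therefore comes from unequal miss rates, with a baseline fixed at present as the extreme case.

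**4. What 4 cleared patients say about the arms.** Fisher's exact test with 16 v 15:

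- 2/16 v 2/15: p = 1.00
- 3/16 v 1/15: p = 0.60
- 4/16 v 0/15: p = 0.10
- 0/16 v 4/15: p = 0.043

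Only the split with all four in the arm of 15 falls below 0.05. For 3/16 v 1/15 the risk difference is 0.1875 − 0.0667 = 0.121. The Wilson limits are 0.066 to 0.430 and 0.012 to 0.298, and the Newcombe 95% interval is:

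- lower: 0.121 − sqrt((0.1875 − 0.066)² + (0.298 − 0.0667)²) = −0.14
- upper: 0.121 + sqrt((0.430 − 0.1875)² + (0.0667 − 0.012)²) = 0.37

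**The case against.** Several points on the other side have force.

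- **The t-test may not be meant for this endpoint.** Present/absent is categorical, and section 11.0 says categorical data are tabulated. Section 10.0 also has lesions measured, so the t-test may be meant for a continuous variable. A reader might infer that the plan requires the t-test here; the text does not settle it. Under the tabulation reading the endpoint has no test at all, and the missing between-arm comparison remains.
- **Baseline presence is not a rule.** A reader might take the lamella to be present at baseline by definition. Eligibility requires only a DSAP diagnosis, and no lesion-selection rule asks for a visible lamella. Presence is inferred from the disease description and the word clearance.
- **The inflation is conditional.** It disappears when miss rates are equal and independent at the two visits, and at a 5% week-12 miss rate it is slight even with a perfect baseline. The documents give no miss rate. They do make unequal rates plausible: dermoscopy is scheduled at baseline only, section 3.0 says it shows structures the naked eye cannot see, and week-12 images may be emailed by patients.
- **The SAP does compare arms on something called lesion clearance.** Its primary outcome carries that label and includes rim elevation. This stands, so it would be wrong to say that no clearance measure is compared. But a 0-4 rim grade inside a composite is not lamella clearance, which the protocol lists separately.
- **Several lesions per patient are possible.** Section 10.0 allows this, and the reading could then be a proportion, to which the k = 4 calculation does not apply.

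**Conclusion.** The firm part needs no assumptions: a listed protocol endpoint has no analysis in the SAP, and neither document compares the randomised arms on it.

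The false-positive part is conditional. It requires that the paired t-test be applied to present/absent readings and that lamellae be missed more often at week 12 than at baseline. Under the stated assumptions the chance of a spurious significant result runs from about nominal to 89%, depending on miss rates that the documents do not give. A reader might infer that the plan would declare clearance significant whatever the drugs do; the equal-miss-rate case, at 3% to 5%, shows that this goes too far.

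This should be corrected. It concerns a listed efficacy endpoint, not the SAP's primary outcome.

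**What to change.** In protocol 11.0, state that the paired t-test does not apply to cornoid-lamella clearance. Add to SAP 4.2 and 6.2:

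- **Comparison:** among patients with lamella present at baseline, the proportion with lamella absent at week 12, cholesterol/lovastatin against lovastatin alone, as a risk difference with a 95% Newcombe interval and an exact test.
- **Image:** the clinical photograph at both visits, since it is scheduled at both and dermoscopy is not.
- **Reading:** by the two blinded DSAP-GASI graders. Researchers are otherwise unmasked, and a miss rate that is the same in both arms creates no between-arm difference only if readers do not know the arm.
- **Per-patient rule:** one rule fixed in advance, for example cleared only if all selected lesions are clear.
- **Within-arm results:** clearance proportions with intervals and no p-value against baseline.

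The cost is wording in two documents, a masked lamella reading of photographs already scheduled, and one two-group analysis. Patients whose lamella is not visible on the baseline photograph leave the denominator. With about 15 per arm the interval will be wide, as the −0.14 to 0.37 example shows, and the result will look less favourable than a before-after p-value.

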12.0 Withdrawal of Subjects

1. Any adverse effect during patient's treatment will require a thorough review of the adverse event by the study team members. Depending on the severity of the adverse event, the participant may be recommended to withdrawal from the study. The research team will continue to follow the patient until resolution of said adverse event has resolved.
2. Upon subject's verbal notification, the study team will evaluate the adverse event, they will proceed to document it and evaluate for subject safety. They will determine if subject is suitable to continue in the study.
3. Information will be provided about safe discontinuation of the drug and if any clinical review needs to occur. For evaluation and reporting purposes, researchers may conduct an exit interview and ask subjects about the reason for early withdrawal.
4. Subjects can participate in the study as long as they want. Subjects may verbally notify investigators if they wish to voluntarily withdrawal from the study and they will be removed immediately.

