13.0 Risks to Subjects

- We anticipate minimal side effects and local irritation to be minimal. Muscle toxicity is a known adverse effect of statins. Patients will be notified during enrollment to watch out for common signs and symptoms such myalgias, fasciculations, cramping, myopathy and increased levels of CK. If an adverse event occurs, the subject must notify the study team members at their earliest convenience. Upon the subject's verbal notification to the study team, the study team will evaluate the adverse event and will proceed to document it and evaluate for subject safety. They will determine if subject is suitable to continue in the study.

- If there is an increased frequency of any concerning adverse event in particular, all enrolled participants in the trial will be sent an individual notice.
- There is a risk for possible breach of confidentiality as photographs of face may be taken to assess lesions on the head. However, all measures to keep information protected will be taken.
- There is a risk of emotional discomfort while the subject takes the questionnaires.
- A cumulative data assessment will be conducted every other month throughout the study's duration by study team members. A report that includes any available efficacy data, as well as a record of anticipated adverse events, will be compiled and submitted to the IRB at that time. Any event meeting the criteria of an unanticipated problem involving risks to subjects or others will be immediately reported to the MUSC IRB, as required by HRPP 4.7- Unanticipated Problems and Adverse Events Policy and Procedures.
- The plan for subject safety and minimizing risks of the research is as follows:
Inspection of the treatment site at each visit. Adverse effects of topical lovastatin/cholesterol will be specifically assessed at each research visit by the investigator, per outlined procedures. Participants are encouraged to reach out to the study coordinator if they think they are experiencing any adverse events. Other expected adverse effects deemed intolerable by the patient will prompt reduction in the patient's dose and treatment if indicated. Any condition necessitating cessation of the study drug will be followed to resolution.

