5.1 Populations

Intention-to-treat (ITT)

All randomized study subjects.

Per Protocol (PP)

All randomized study subjects completing the whole study period (complete cases). For a specific analysis, study subjects with missing data on any of the variables in the model will be excluded from the analysis. Analyses of this population is seen as a sensitivity analysis to investigate whether conclusions are sensitive to assumptions regarding the pattern of missing data.

6. Analysis

All enrolled subjects are considered in the demographic data and safety analysis. Treatment efficacy is based on investigator-standardized patient-documented photographs. Repeat photo documentation will be obtained if image quality was inadequate or angle, lighting or location is not standardized to prior photos.

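### Protocol 12.0 does not separate stopping the ointment from leaving the study and plans no outcome collection after stopping, so the 12-week comparison may be informatively missing

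*Protocol*

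**What the plan says.** Early exit is governed by Protocol section 12.0. After an adverse event: "Depending on the severity of the adverse event, the participant may be recommended to withdrawal from the study". The same section has the team decide whether the subject is fit to carry on in the study. What follows such an exit is safety follow-up: "The research team will continue to follow the patient until resolution of said adverse event has resolved".

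Stopping the drug is mentioned in 12.0 only in passing: "Information will be provided about safe discontinuation of the drug and if any clinical review needs to occur". The next sentence says that "researchers may conduct an exit interview and ask subjects about the reason for early withdrawal". On voluntary exit: "Subjects may verbally notify investigators if they wish to voluntarily withdrawal from the study and they will be removed immediately".

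Protocol section 13.0 does name cessation of the drug: "Any condition necessitating cessation of the study drug will be followed to resolution". It also allows treatment to be reduced for effects that the patient finds intolerable.

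On masking, Protocol section 10.0 states: "Researchers will not be masked". The schedule of events in that section sets photographs and scales at baseline and weeks 4, 8 and 12.

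In the SAP, section 4.1 puts the primary outcome at 12 weeks, and section 5.1 defines the intention-to-treat set as "All randomized study subjects". Section 6.1 restricts the DSAP-GASI efficacy analysis to participants with clear photographs at all visits. Section 7 removes patients who did not submit photographs and excludes missing data.

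**The concern.** Stopping a topical treatment and leaving a trial are different events. A patient can do the first and still send photographs and fill in scales. Section 12.0 does not draw that line, and no section says what outcome data are wanted from someone who has stopped.

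The SAP makes this matter. Under the all-visits rule, one missed visit removes the patient's whole efficacy record, including photographs already taken. If patients who stop because of intolerance or lack of benefit are lost, the patients analysed are a selected group. Staff who know the arm advise on withdrawal, so the selection could differ by arm. The two blinded graders in SAP 6.1 protect the scoring of photographs, but they have no influence on whose photographs reach them.

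The two SAP sets are affected as well. Section 5.1 treats the complete-case set as a sensitivity check on missing-data assumptions. That check tells the reader little if week-12 outcomes exist only for patients who completed.

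**Working it through.** **Reading the provisions together**

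- Adverse event (Protocol 12.0): the exit named is from the study. Follow-up is tied to resolution of the event, not to week 12 and not to photographs or scales.
- Cessation of drug (Protocol 13.0): named apart from study withdrawal. Follow-up is again of the condition.
- Request to leave the study (Protocol 12.0): removal at once.
- Stopping the ointment without asking to leave: not addressed.
- Reason for leaving (Protocol 12.0): optional. No final photograph or scale is listed at exit.
- Primary analysis (SAP 6.1 and 7): photographs at all visits are required.

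A patient who leaves under 12.0 as written therefore contributes nothing to the primary analysis.

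**Size**

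The documents state no discontinuation rate, reasons, split by arm, SD, alpha or power, so there is no figure of the plan's to reproduce. What follows illustrates on assumed inputs. The documented inputs are 31 enrolled (SAP 2.1) and 1:1 allocation (Protocol 10.0), or 31/2 = 15.5 per arm.

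1. One exit is 1/15.5 = 6.5% of an arm.

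2. Bias in score points. Let a share *d* of an arm leave, and let leavers improve by *g* points less than stayers. The stayers' mean exceeds the arm's true mean by *d* × *g*, and the bias in the contrast is the difference of these products between arms.
   - Equal loss and equal *g*: 0.
   - 30% v 10% loss with *g* = 0.5 to 1.0: (0.30 − 0.10) × 0.5 = 0.10, up to (0.30 − 0.10) × 1.0 = 0.20 points.
   - 20% loss in both arms: no bias in the contrast, but each arm's own improvement from baseline is overstated by 0.20 × 0.5 = 0.10 to 0.20 × 1.0 = 0.20 points. That affects the paired before-after comparison in Protocol 11.0.

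3. Bias in SD units, one-sided loss. Suppose 20% of one arm leave (0.20 × 15.5 = 3.1, about 3 patients), nobody leaves the other arm, and there is no true difference.
   - Leavers are exactly the worst responders (correlation 1): φ(0.8416)/0.80 = 0.280/0.80 = 0.35 SD in favour of the arm with the loss. This is a large-sample formula.
   - Correlation 0.5 between stopping and poor response: 0.5 × 0.35 = 0.175, about 0.17 SD.
   - Correlation 0: 0.

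4. Precision. With assumed two-sided alpha 0.05 and 80% power, the detectable difference is (1.96 + 0.8416) × √(2/n) for n per arm. At n = 15.5 it is 1.01 SD. At 20% overall loss (31 × 0.8 = 24.8, about 25 patients, n = 12.4) it is 1.13 SD.

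**The case against.** A reader might infer that the protocol makes stopping the ointment the same as leaving the study, that patients who stop by choice are removed, and that the week-12 endpoint is selectively missing. The documents do not support any of these as stated.

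- Section 12.0 says only that withdrawal may be recommended, depending on severity. It does not equate stopping with leaving.
- The removal sentence covers patients who ask to leave the study, which is ordinary voluntary withdrawal.
- The visit schedule is not conditional on being on treatment. Section 13.0 names cessation and reduction apart from withdrawal. Compliance is asked about at the check-ins, and SAP 4.2 records application frequency, so imperfect users are evidently expected to stay under observation.
- The protocol anticipates minimal side effects. Both arms contain lovastatin, and the muscle toxicity it names is attributed to statins, so unequal loss from that cause is not evident.
- With equal loss and equal shortfall, the contrast is not biased.
- The all-visits rule is itself a main cause of exclusion. With 12.0 rewritten, a patient missing one photograph would still be dropped.
- SAP 2.1 reports enrolment in the past tense, so an amendment may come too late for some or all of the 31.

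All of this stands, and it limits the point to an unaddressed case and a risk. It does not close the gap: where the text is silent, collection after stopping is left to unmasked staff, case by case. The one exit that 12.0 does state after an adverse event is from the study.

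**Conclusion.** The point holds as a gap in data collection that is cheap to close. Section 12.0 does not distinguish stopping treatment from withdrawing, provides for no outcome collection after stopping, and leaves the reason optional. Joined to SAP 6.1 and 7, this means that early leavers fall out of the primary analysis and that the intention-to-treat set in SAP 5.1 cannot be analysed as defined.

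Missingness may be informative; the documents do not show that it is. The between-arm bias runs from 0 to about 0.17–0.35 SD. The upper range needs 20% loss confined to one arm and a correlation of 0.5 to 1 between stopping and poor response. Those inputs are assumptions, and nothing in the documents says which end of the range is nearer.

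**What to change.** In Protocol 12.0, separate stopping study drug from withdrawing consent for follow-up. State that a patient who stops the ointment but does not withdraw consent is asked for the remaining scheduled photographs and scales and stays in the efficacy analysis in the randomized arm. Record the date and reason for stopping for every patient, as far as the patient is willing to give it, in place of the optional exit interview.

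In SAP 6.1 and 7, replace the all-visits rule with an analysis of all available visits, for example a likelihood-based repeated-measures model, with a sensitivity analysis for missing data. Without this the change to 12.0 does not deliver the set defined in SAP 5.1.

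If follow-up of the 31 patients is already closed, report losses by arm and reason, analyse all available visits, and state that collection after stopping was not planned.

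The cost is a short protocol and consent amendment and a SAP edit. Visits are virtual and photographs can be sent remotely, so no new procedure or staff is needed. Some patients who stop will decline, and off-drug values may dilute the contrast between arms. When or whether treatment is stopped or reduced is a clinical matter and is left as it is.
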